7.6.7.1. Evaluation of Effectiveness

A claims-based algorithm with high specificity for fracture site developed by Wright et al ([Wright et al, 2019](#)) will be used to identify osteoporosis-related fractures (see Appendix 2). Case qualifying (CQ) fractures are those identified during an inpatient hospital stay, in any position on the medical claim, or in an outpatient setting accompanied by a fracture repair procedure code. Validation of this algorithm was done using International Classification of Diseases, 9th Revision (ICD-9) codes before the Healthcare System in the USA switched to the ICD-10 system. In a separate study, Wright et al mapped the ICD-9 codes to ICD-10 codes in an evaluation of hip fracture trends in the Medicare data. The results from that study did not suggest that the ICD-10 version systematically identified a higher or lower number of fractures than the ICD-9 codes.

The evaluation period for nonvertebral fracture events will start from the index date (date of initial prescription dispensed) to the earliest of the following events:

- a) First non-vertebral fracture event date (hip, pelvis, shoulder, radius or ulna, wrist, femur, tibia or fibula, ankle)
- b) 18 months after the index date
- c) In-hospital death

The evaluation period for hip fracture events will start from the index date (date of initial prescription dispensed) to the earliest of the following events:

- a) first hip fracture event date
- b) 18 months after index date
- c) In-hospital death

7.6.7.2. Evaluation of Cardiovascular Safety

Evaluation of cardiovascular safety outcomes will be carried out for patients who have 18 months of follow-up data from their index date while on treatment with ABL or TPTD. The following data variables will be extracted:

- End of treatment date which is the last prescription date + supply day
- Date of the first incidence of MI
- Date of the first incidence of stroke
- Date of the first incidence of heart failure
- Date of in-hospital cardiovascular death
- Date of all-cause in-hospital death

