The comparative evaluation of treatment options is ideally done within the controlled clinical study setting. The current study is observational, and treatments are not assigned. As such, randomization is not possible. Although this is not a randomized study, PS matching will be used to define the study cohorts and provide confidence that the 2 treatment groups are comparable in their probability to receive and benefit from treatment. Patients will be matched on all indicators of disease severity and fracture risk including prior disease and treatment history. Furthermore, patients will also be matched on history of falls as well as comorbid conditions and concomitant medications associated with increased fall risk or with bone quality and strength. While several comorbidities were initially considered, some measures were ultimately not included in the end due to lack of available data. This includes duodenitis. Lastly, there could be residual confounding despite matching. The study is planned as an intention-to-treat (ITT) analysis for effectiveness evaluation and as-treated (AT) analysis for safety evaluation with additional consideration for duration of treatment exposure using sensitivity analyses on various length of observed treatment duration for the study cohorts. Interpretation is limited by the variable length of follow-up.

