7.3. Duration of Subject Participation

Because this is a retrospective claims-based cohort study, subjects included in the analyses will not actively participate in the study and no study visits will be required. The study will use anonymized patient data.

Both effectiveness and cardiovascular safety outcomes will be assessed for patients with 18 months of follow-up data from their index date.

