7.6.7. Outcomes

Both effectiveness and cardiovascular safety outcomes will be assessed for patients with 18 months of follow-up data after their index date. Cardiovascular safety outcomes will be evaluated during the treatment period which is from index date to the last prescription anabolic drug possessed within the 18 months after the index date, regardless of the anabolic drug possession gap between any 2 prescription fills.

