7.8.3. Analysis Populations

Analysis population are all patients meeting the study inclusion/exclusion criteria and selected after propensity matching. The same matched population will used for both effectiveness and safety analysis.

The effectiveness evaluation will be conducted using an ITT analysis, meaning that the first fracture event during the 18 months (+ 30 days follow-up) after the index date will be summarized regardless of when treatment ended. Cardiovascular safety outcomes will be evaluated using an As-Treated (AT) analysis based on only events occurring during the treatment period which is from the index date to the last prescription anabolic drug obtained within the 18 months after the index date, regardless of the anabolic drug possession gap between any 2 prescription fills.

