7.8.6. Effectiveness Analyses

In this study, the primary analyses of effectiveness will be noninferiority analyses for ABL versus TPTD on time to the first incidence of nonvertebral fractures with a margin of 30%. Noninferiority of ABL to TPTD will be concluded if the upper bound of 2-sided 95% CI of HR between ABL versus TPTD is < 1.3.

In a recently published historical control observational study evaluating the real-world effectiveness of osteoporosis therapies using Medicare claim data between 2008 and 2011, the fracture incidence rates for the 12-month pre-treatment period were compared with the 12-month on-treatment period ([Yusuf et al, 2018](#)). For patients treated with TPTD, the incidence rate ratio (IRR [95% CI]) was 0.36 (0.31 to 0.41) for any fracture and 0.34 (0.32 to 0.36) for hip fracture. Based on the EMA and FDA noninferiority margin guidelines ([EMA, 2005](#); [FDA, 2016](#)), if the upper boundary of ABL versus TPTD is $HR < 1.3$, then ABL will preserve approximately 70% of the TPTD benefit, which is higher than the minimum required threshold of 50%.

Comparisons of the time to fracture between the PS-matched ABL and TPTD groups will be based on a Cox proportional hazards model. The hazard ratio (HR) and 95% confidence interval (CI) between the 2 treatment groups will be calculated. The Kaplan-Meier method will be used to estimate event rates. Log rank test will be calculated.

For the fracture outcomes, and the corresponding sensitivity and subgroup analyses, patients will be followed for up to 18 months or until their first fracture event (for the fracture site of interest under evaluation), whichever comes first. All analyses are based on index medication cohort.

The duration, in days, from the date of the first filled prescription for ABL or TPTD to the first incidence of nonvertebral fracture will be derived. If a patient does not experience any nonvertebral fractures during the 18 months of treatment + 30-day follow-up (for a total of 19 months), the patient will be censored at the day of in-hospital death or the 19 months.

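### Three sections limit outcome assessment to women with 18 months of follow-up data, contradicting the rules that keep women who die or stop early

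*Combined protocol and SAP*

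**What the plan says.** Three places attach a condition to the patients in whom outcomes are assessed:

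- Section 7.3: "Both effectiveness and cardiovascular safety outcomes will be assessed for patients with 18 months of follow-up data from their index date".
- Section 7.6.7: outcomes "will be assessed for patients with 18 months of follow-up data after their index date".
- Section 7.6.7.2: the cardiovascular evaluation "will be carried out for patients who have 18 months of follow-up data from their index date while on treatment with ABL or TPTD".

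Other places follow a different rule:

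- Table 1 (Section 7.4.1) asks for claims activity before the index date only. Neither Table 1 nor Table 2 mentions survival, follow-up or treatment duration after it.
- Section 7.8.1.1 analyses everyone who passes the eligibility criteria. Section 7.8.3 takes all eligible patients selected by matching and adds "The same matched population will used for both effectiveness and safety analysis".
- For fractures, Section 7.6.7.1 ends the evaluation period at in-hospital death. Section 7.8.6 says that, without a fracture, "the patient will be censored at the day of in-hospital death or the 19 months".
- For cardiovascular safety, Section 7.6.7.2 itself extracts the "Date of in-hospital cardiovascular death". Section 7.8.7 includes those deaths and counts events until 30 days after treatment ends.
- Section 7.8.10.1 removes women with short exposure only in sensitivity analyses.
- Section 7.1.3 concedes: "Interpretation is limited by the variable length of follow-up".

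**The concern.** The three sentences are worded as a criterion for patients, not as a maximum length of observation. A woman who dies in hospital in month 4 does not have 18 months of data. Applied as written, the condition selects on something that happens after the index date, namely survival to month 18.

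In-hospital cardiovascular death is a component of both secondary composites, so the safety analysis has most to lose. The primary analysis is touched too. A woman who fractures a hip and then dies in hospital before month 18 would leave the set together with her fracture, and Section 5.3 itself links hip fracture to mortality.

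A programmer could plausibly apply the sentences as a filter, because this plan already selects on post-index information: Table 2 excludes women who switch anabolic drug within 18 months. The plan also does not define what having 18 months of data means in a source whose medical claims are open and unadjudicated (Section 7.5). A literal filter could therefore also remove women who simply generate no late claims.

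**Working it through.** The plan gives no power or event figure for cardiovascular safety. Its one design figure, 95% power for fracture noninferiority, does not enter this check.

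**1. The two sets of rules applied to the same patient**

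| Patient | Sections 7.6.7.1, 7.8.3, 7.8.6, 7.8.7 | 18-month condition as a filter |
|---|---|---|
| In-hospital cardiovascular death in month 4, on drug | Composite event; censored for fracture if none has occurred | Not assessed |
| Hip fracture in month 5, in-hospital death in month 6 | Primary event in month 5 | Not assessed; fracture lost |
| Stroke in month 3 on drug, then stops, has data to month 18 | Composite event | Kept under 7.3 and 7.6.7; under 7.6.7.2 it depends on how the on-treatment phrase is read |

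The first two rows cannot be programmed both ways.

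**2. Does the calendar require a follow-up condition?** Inputs: last index date 30 June 2019 and data end 31 January 2021 (Table 3); 1 month = 30 days (Section 7.8.6).

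- 18 months = 18 × 30 = 540 days. 30 June 2019 + 540 days = 21 December 2020.
- 18 months + 30 days = 570 days. 30 June 2019 + 570 days = 20 January 2021.
- 30 June 2019 to 31 January 2021 = 581 days, which leaves 581 − 570 = 11 days.

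Every index date has the full window before the data end. As a statement about the calendar, the condition removes nobody. If it removes anyone, it does so through death, absent claims or stopping treatment.

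**3. Size if it were used as a filter.** The documents give no cardiovascular death rate, so a range is assumed: 0.05% to 0.5% over the window, in 16,000 women.

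- 16,000 × 0.0005 = 8 deaths; 16,000 × 0.005 = 80 deaths.
- Under the filter, about 0 remain. The only survivors of the rule would be deaths after day 540: exposure is capped at day 540 (Section 7.8.8), so the 30 days in Section 7.8.7 could reach day 570.

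For the composite without heart failure, take the pivotal-study proportions in Section 6.2.3 as a stand-in (0.5% abaloparatide, 0.6% teriparatide):

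- 8,000 × 0.005 + 8,000 × 0.006 = 40 + 48 = 88 events.
- If 10% to 40% of them were such deaths (assumed), 88 × 0.9 = 79 to 88 × 0.6 = 53 would remain.

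These are illustrations. Claims-based rates and a shorter on-treatment window would change the counts. That deaths before day 540 fail the filter does not depend on the rates.

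**The case against.** The strongest reply is that 18 months was meant as an observation window. On that reading the three sentences fit with everything else. The calendar check supports it, and the operative sections (eligibility tables, analysis population, censoring, event window) all keep women who die or stop. Section 7.6.7.2 extracts death and end-of-treatment dates, which would serve little purpose in a set of 18-month completers. This reply largely stands as to intent. It does not settle the matter, because the sentences still say something else and the plan never states which reading governs. For fractures an explicit censoring rule counters them. For cardiovascular events Section 7.8.7 gives a window but no censoring list.

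Three stronger conclusions that a reader might draw are not supported:

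- *That the plan does drop early deaths.* The rules listed above include them, so the loss occurs only if the condition is programmed as a filter.
- *That the safety set consists of women who stay on drug for 18 months, and so shrinks sharply.* The on-treatment phrase most naturally mirrors the endpoint definition in Section 5.2. Section 7.6.7 defines the treatment period as running "from index date to the last prescription anabolic drug possessed within the 18 months after the index date", which may be short. Women with little exposure are removed only in sensitivity analyses. The documents give no persistence figure from which to size such a loss.
- *That the loss would differ between arms because the heart-rate effects differ (7.9 versus 5.3 bpm, Section 6.2.3).* Heart rate says nothing direct about persistence or death, and the same section reports similar serious cardiac events and 0.5% versus 0.6% for major events.

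**Conclusion.** The point holds as an internal contradiction. Sections 7.3, 7.6.7 and 7.6.7.2 state a condition on patients that cannot be applied together with Table 1, Sections 7.6.7.1, 7.8.1.1, 7.8.3, 7.8.6 and 7.8.7, and the short-exposure analyses in Section 7.8.10.1.

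The condition is either redundant (read as calendar availability) or harmful (read as a filter). In the harmful case the analysis conditions on survival: nearly all in-hospital cardiovascular deaths leave both secondary composites, and fractures followed by in-hospital death before month 18 leave the primary analysis. The 8 to 80 deaths rest on an assumed risk. How many fractures would be lost cannot be worked out from the documents, and neither the direction nor the existence of a between-arm bias is shown. Because one available reading nearly empties a safety component, the wording should be settled before the analysis cohort is built.

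**What to change.** In Sections 7.3, 7.6.7 and 7.6.7.2, replace the condition with text such as: *Outcomes will be assessed in all matched patients from the index date; 18 months is the maximum observation window (plus the 30-day follow-up where 7.8.3, 7.8.6 and 7.8.7 apply it), and no minimum post-index survival, follow-up or treatment duration is required.*

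In Section 7.6.7.2, state that the on-treatment phrase limits the period in which events count and does not select patients.

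In Section 7.8.7, add a censoring rule parallel to the fracture rule: follow-up ends at the earliest of the event, a recorded in-hospital death, or the end of the as-treated window including its 30 days. The word *recorded* matters because deaths outside hospital are not captured (Sections 7.1.3 and 7.5).

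The cost is wording in four sections and a check that the cohort program applies no post-index data filter. No new data are needed.

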7.7. Data Management

For this study there will be no new primary data collected. The study will be conducted using real-world (secondary) data for analysis. [REDACTED] software will be used to connect to the Cloudera Hadoop (CDH) 7.1.4-1 database for data extraction. R software may be used for PS matching. Datasets and tables, figures, and listings (TFLs) will be created on a Citrix Windows platform using SAS V9.4 M6.

7.8. Statistical Methods and Analyses

The study will use a convenience sample of patients who meet the study selection criteria. Medical and pharmacy claims will be used to determine the presence of conditions. International Classification of Diseases Clinical Modification, 9th Revision (ICD-9-CM) and 10th Revision (ICD-10-CM) codes will be used to assess comorbidities. National Drug Code (NDC) codes will be used to identify the anabolic drug (ABL or TPTD) and to identify prior and concomitant medications. Additionally, the Current Procedural Terminology (CPT) and Healthcare Common Procedure Coding System (HCPCS) will be used to support the derivation.

Detailed code lists are included in Fracture Algorithm ([Appendix 2](#)), Cardiovascular Event Codes ([Appendix 3](#)), Diagnostic Codes for All Comorbidities ([Appendix 4](#)), and NDC Codes and HCPCS Codes for Medications ([Appendix 5](#)).

7.8.1. Power and Sample Size

7.8.1.1. Sample Size

All patients who meet the inclusion criteria and do not meet any of the exclusion criteria will be included in the analysis. After PS matching, it is estimated that approximately 16,000 patients will be included in the analyses, 8,000 patients in each cohort.

7.8.1.2. Power Calculation

- Abaloparatide versus teriparatide with a noninferiority margin of 30%
 - Assuming a nonvertebral fracture rate of 3.5% at the end of 18 months
 - 8,000 matched subjects in each group
 - 95% power for HR up to 1.3

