6.2.3. Abaloparatide

Abaloparatide is a chemically synthesized analog of the first 34 amino acids of human parathyroid hormone-related peptide [hPTHrP(1-34)] that is anabolic in bone. Secondary pharmacological effects of ABL include transient and reversible increases in heart rate after injection, with associated AEs of palpitations and tachycardia observed in the pivotal clinical study. A post-hoc analysis was performed to examine the effects of treatment on heart rate, blood pressure, and cardiovascular-related AEs, including MACE with or without heart failure in the ACTIVE/ACTIVExtend study ([Cosman et al, 2020](#)). ABL and TPTD transiently increased heart rate relative to placebo. After the first dose, the mean (SD) change in heart rate from before treatment to 1 hour after treatment was 7.9 (8.5) bpm for ABL, 5.3 (7.5) bpm for TPTD, and 1.2 (7.1) bpm for placebo. A similar pattern was observed over subsequent visits. The corresponding change in mean supine systolic and diastolic blood pressure 1 hour after treatment was -2.7/-3.6 mmHg for ABL, -2.0/-3.6 mmHg for TPTD, and -1.5/-2.3 mmHg for placebo. The percentage of participants with serious cardiac AEs was similar across the treatment groups (0.9% and 1.0%). In a post-hoc analysis, the percentage of participants with MACE during the ACTIVE study was 0.5% in the ABL group, 0.6% in the TPTD group, and 1.2% in the placebo group; MACE + heart failure increased the proportion in the placebo group to 1.7%. Time-to-first incidence of MACE + heart failure was significantly longer for ABL compared with placebo ($p = 0.02$) and for TPTD compared with placebo ($p = 0.04$; [Cosman et al, 2020](#)). During the 2-year ACTIVExtend period, the incidence of MACE, with or without heart failure, was similar between the placebo/alendronate and ABL/alendronate groups leading to the conclusion that ABL was associated with transient increases in heart rate and small decreases in blood pressure in postmenopausal women with osteoporosis, with no increase in risk of serious cardiac AEs, MACE, or heart failure.

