This study will be conducted by PRA Health Sciences using this prespecified protocol and statistical analysis plan. In the absence of randomization, this observational study will use propensity score (PS) matching for comparative evaluation of safety in addition to effectiveness outcomes. Further quality control work has been performed on the data including the assignment of codes. The study has reasonable power to show comparable effectiveness and safety profile between the 2 active treatment arms.

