For the fracture outcomes, an ITT analysis will be applied. Patients will be followed for up to 18 months + 30-day follow-up, or until their first fracture event (for the fracture site of interest under evaluation) or in-hospital death, whichever comes first. Duration, in days, from the index date to the last follow-up date will be calculated. For calculation purposes, 1 month is equivalent to 30 days. All analyses are based on the patient's index medication cohort.

A nonvertebral fracture is any fragility fracture at the hip, pelvis, femur, ankle, shoulder (including shoulder, humerus, clavicle), radius/ulna, wrist, or tibia/fibula. Derivation details are provided in [Appendix 2](#).

The time to the first incidence of hip fracture and the other 7 individual fracture sites will be summarized using similar methods as those used for nonvertebral fracture.

The Kaplan-Meier curves will be generated to graphically display the fracture event or 18 months plus 30-day follow-up.

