7.8.7. Safety Analyses

A Cox proportional hazards model will be used for the time to first cardiovascular event. HR and 95% CIs will be presented.

The ICD-10 diagnosis from the hospital claim and physician claim will be used to derive post-index myocardial infarction (MI) (I21.x, I22.x), stroke (I61.x – I63.x), or heart failure (I50.x, excluding I50.x2, I50.8x). Hospital discharge status code (20 to 29 or 40 to 42) will be derived for in-hospital death. A detailed code list is provided in [Appendix 3](#). Subjects with in-hospital cardiovascular death derived from indirect approach 2 ([Xie et al, 2018](#)) will be included in the analyses. 2018 ICD-10 CM and General Equivalence Mappings (GEMS) from the Centers for Medicare & Medicaid (CMS) ([will be used to translating ICD-9 CM to ICD-10 CM \(CMS, 2018\)](#)).

The As-Treated (AT) analysis will be conducted for the safety evaluation. The first incidence of a cardiovascular event after the index date and before the 30 days after the end of treatment will be analyzed.

A cardiovascular event is the first incidence of the composite endpoint of nonfatal MI, nonfatal stroke, or in-hospital cardiovascular death; the first incidence of the composite incidence of nonfatal MI, nonfatal stroke, heart failure or in-hospital cardiovascular death; or the first incidence of MI, stroke, heart failure, or in-hospital cardiovascular death separately.

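### The stated 95% power does not follow from the planned hazard ratio test; the plan's own inputs give about 87% at a true hazard ratio of 1

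*Combined protocol and SAP*

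**What the plan says.** Section 7.8.1.2 is the plan's only power calculation. It sets a 30% noninferiority margin and 8,000 matched subjects per group, adds "Assuming a nonvertebral fracture rate of 3.5% at the end of 18 months", and concludes "95% power for HR up to 1.3". It names no true HR, alpha or formula.

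Section 7.8.6 defines the test. A Cox model compares the matched groups, and noninferiority is concluded "if the upper bound of 2-sided 95% CI of HR between ABL versus TPTD is < 1.3". This is a one-sided test at 2.5% on the HR scale. The same section sets the follow-up: "Patients will be followed for up to 18 months + 30-day follow-up, or until their first fracture event". It counts a month as 30 days, so the window is 570 days, against 540 days for 18 months.

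Section 6.3 makes a wider claim: "The study has reasonable power to show comparable effectiveness and safety profile between the 2 active treatment arms". For safety, section 7.8.7 plans estimation only: "HR and 95% CIs will be presented". Neither section gives a safety margin, an expected event count or a power figure.

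**The concern.** The power of a Cox noninferiority test is driven by the number of events. About 560 events looked too few for 95% power against a margin of 1.3 if the two drugs are truly equal.

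The wording adds to the doubt. Read literally, it promises 95% power for true HRs up to 1.3. At a true HR of 1.3 the chance of passing is 2.5%, so 1.3 can only be the margin, and the true HR behind the figure is left unsaid.

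What is at stake is interpretation. If noninferiority is not shown, readers will judge that against a stated 5% chance of missing it. For safety, the sentence in section 6.3 invites readers to take a confidence interval that includes 1 as evidence of comparability, with no stated precision behind it.

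**Working it through.** **Inputs.** From 7.8.1.2: 8,000 per group, a 3.5% rate at 18 months and a margin of 1.3. From 7.8.6: a 2-sided 95% interval for the HR (z = 1.96), with 19 months as the alternative window. Assumed here: a true HR of 1, the usual choice for noninferiority, and no dropout.

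**Trying to reproduce 95% with the planned test**

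1. Events: 2 × 8,000 × 0.035 = 560.
2. Power at a true HR of 1: Φ(ln(1.3) × √(events/4) − 1.96). Here ln(1.3) = 0.26236, and 0.26236 × √140 − 1.96 = 1.144, so power is 87.4%.
3. Cross-checks: Freedman's formula gives 87.0%. Simulations (20,000 runs each) give 87.4% and 87.5%.
4. 19-month window: 1 − 0.965^(570/540) = 3.69%; 16,000 × 3.69% is about 591 events; power is 89.0%.

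The 95% is not reproduced.

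**What 95% would need on the HR scale**

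- Events: 4 × (1.96 + 1.645)² / 0.26236² ≈ 755. That is about 4.7% per arm with 16,000 patients, or about 21,600 patients at 3.5%.
- Or a true HR of about 0.96: 0.959 with events held at 560, and 0.955 with TPTD held at 3.5% and ABL events reduced to match.

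With 560 events, the largest observed HR that passes is exp(0.26236 − 1.96 × √(4/560)) ≈ 1.10.

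**Sensitivity to the unstated or uncertain inputs**

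| Change (others as above) | Events | Power |
|---|---|---|
| Fracture rate 3.0% | 480 | 82.0% |
| Fracture rate 4.0% | 640 | 91.3% |
| True HR 0.90 | 532 | 98.9% |
| True HR 0.95 | 546 | 95.6% |
| True HR 1.05 | 574 | 72.5% |
| One-sided 5% instead of 2.5% | 560 | 92.8% |

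**Calculations that reach 95% but are not the planned test**

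- Noninferiority on the risk difference, with margin 0.30 × 3.5% = 1.05 percentage points: 0.0105 / √(2 × 0.035 × 0.965 / 8,000) − 1.96 = 1.653, which is 95.1%. This formula asks for 7,962 per group at 95% power, very close to 8,000.
- Detecting an HR of 1.3 at one-sided 5%, with ABL events counted at that HR: 8,000 × (0.035 + 1 − 0.965^1.3) ≈ 642 events, which is 95.3%.

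The first is the closest match, but whether either was used is an inference.

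**Safety precision.** The plan gives no expected rate, so this assumes that the ACTIVE percentages for major adverse cardiovascular events (MACE) in section 6.2.3 carry over. There, "the percentage of participants with MACE during the ACTIVE study was 0.5% in the ABL group, 0.6% in the TPTD group". Placebo patients had higher figures: 1.2% for MACE alone, rising to 1.7% once heart failure is counted. The interval around an HR of 1 is exp(±1.96 × √(4/events)).

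| Assumed rate | Events | 95% interval |
|---|---|---|
| 0.5% ABL, 0.6% TPTD | 40 + 48 = 88 | 0.66 to 1.52 |
| 1.2% in both arms (placebo MACE) | 192 | 0.75 to 1.33 |
| 1.7% in both arms (placebo MACE + heart failure) | 272 | 0.79 to 1.27 |

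As-treated follow-up and 60% capture of inpatient events (section 6.3) could lower these counts. The less healthy population expected in section 7.1.4 could raise them.

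**The case against.** The strongest reply is that the 95% is under-specified rather than shown to be wrong. The plan states no true HR, and the planned test does reach 95% if ABL is slightly better than TPTD. If the figure came from the risk-difference calculation, its arithmetic is sound and the fault is a mismatch of scale with the Cox test. Both points are fair about where the number may have come from. Neither rescues the line as written: it either does not describe the planned test or omits an assumption on which it depends, and both need an edit.

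It can also be said that nothing in the design hangs on the figure. The sample is every eligible patient who can be matched (sections 7.1 and 7.8.1.1), 8,000 is an estimate from previous studies, and Table 3 dates the single data pull to June 2021, before the protocol date of 09 July 2021. The final confidence interval will show the precision achieved. That stands, and it limits the severity. It does not make a wrong power statement for the primary endpoint acceptable when correcting it needs only a text edit.

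On safety, the objection largely stands. Safety is secondary and planned as estimation, so no stated rule is broken by the lack of a power calculation. The intervals above rest on trial rates that may not carry over, and the higher rates come from a placebo arm that is not part of this study. They are illustrations only.

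**Conclusion.** The concern holds. At a true HR of 1, the stated inputs and the stated decision rule give 87.4% power with 560 events and 89.0% with 591, against the 95% claimed. The chance of missing noninferiority when the drugs are equal is therefore about 11% to 13%, more than double the implied 5%. The shortfall of 6 to 8 points rests on a true HR of 1, a 3.5% rate in both arms and no dropout. It would disappear at a true HR of about 0.96.

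This should be fixed, but it does not undermine the design: 87% is adequate, and the decision rule and type I error are unchanged. The conclusion rests on the power line in 7.8.1.2. The unsupported safety wording in 6.3 is a lesser matter of missing detail and would not carry the point alone.

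**What to change.** In 7.8.1.2, replace the power line with text along these lines: *about 87% power (about 560 events over 18 months), assuming a true HR of 1, to show that the upper limit of the 2-sided 95% CI of the HR is below 1.3*. If the calculation is tied to the 19-month window instead, the figures are about 591 events and 89%. If the 95% came from a true HR below 1 or from another method, state that HR or method with its formula and alpha, and say how it relates to the Cox test in 7.8.6.

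In 6.3, drop safety from the power sentence, or give the expected number of events and the confidence interval width for each safety composite.

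The cost is two text edits. Data, matching and analyses stay as they are. The only downside is a less favourable stated power.
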